#### 15 ETHICS/PROTECTION OF HUMAN SUBJECTS

#### 15.1 Potential Risks and Benefits

#### 15.1.1 Potential Risks

The potential risks to participants are minimal.

Surveys: Some participants may be uncomfortable answering personal questions, or feel uncomfortable with the HIV prevention topics. Men will have the option for all questions to not answer.

Disclosure of participation in a research study: There is a possibility that someone participating in an online data collection could be identified as participating in research, but this is uncommon. There is some risk that those who participate in online surveys could be observed if they complete the surveys in public, or that data could be at risk during transmission. We will mitigate this risk by reminding participants at the beginning of each survey to complete the survey in a private place, where their responses cannot be observed by others. We will also encourage participants to delete any emails or text messages received as part of the study to protect them from an unauthorized individual viewing the messages.

#### 15.1.2 Potential Benefits

There are no direct benefits for participating in this study. The potential benefits to study participants in the intervention group include access to HIV and STI testing, knowledge about serostatus, access to pre-exposure prophylaxis for HIV prevention, access to free condoms, ordered by participants through the study app and delivered through a parcel shipping service (e.g., UPS or FedEx), and access to information to promote personal health. Control arm participants might benefit from access to information about HIV prevention services.

#### 15.2 Ethical Standard

The investigator will ensure that this study is conducted in full conformity with the principles set forth in The Belmont Report: Ethical Principles and Guidelines for the Protection of Human Subjects of Research, as drafted by the US National Commission for the Protection of Human Subjects of Biomedical and Behavioral Research (April 18, 1979) and codified in 45 CFR Part 46 and/or the ICH E6.

# 15.3 Institutional Review Board

The protocol, informed consent form(s), recruitment materials, and all subject materials will be submitted to the Emory University IRB for review and approval. Approval of both the protocol and the consent form must be obtained before any subject is enrolled. Any amendment to the protocol will require review and approval by the IRB before the changes are implemented in the study. IRB authorization agreements (IAA) will be used between Emory University and each site.

#### 15.4 Informed Consent Process

Consent will be administered through the online screening and registration portal. Because men will not be enrolled and consented at an "in person" visit, the consent process will be online.

Therefore, a video-based online consent will be used, and the participant will be provided a PDF of the complete informed consent document.

The consent will be done in two stages, for screening and study enrollment. Due to the sensitive nature of screening questions regarding participants' sexual history, all potential participants must consent to be screened before they can access the eligibility survey. The consent to screen form (Appendix A) will describe the nature of the study, the need to collect sensitive sexual health information in the screener, and what safeguards are in place to ensure the security and confidentiality of the screening data collected.

Those determined to be eligible will be directed to an electronic informed consent form (Appendix B) presented online. The electronic informed consent document will explain: (1) what is meant by consent; (2) why we need to obtain consent and (3) the purpose of the consent form. Participants will also have access to a video describing the components of the informed consent document. Participants will be required to view the informed consent document before indicating whether or not they consent; this will be enforced by requiring participants to scroll through the entire consent before they can choose to consent to participate. Consent or lack thereof will be documented in the electronic database by the stored variable indicating consent or lack of consent. A button to allow participants to print or email the consent form for their records will be located at the end of the consent form document. The consent process will take approximately 5 minutes per individual. Study staff will be available during business hours by phone or by email to answer any questions that participants have prior to consenting. The consent forms have a Flesch-Kinkaid Reading Level of <8.5.

# 15.5 Exclusion of Women, Minorities, and Children (Special Populations)

Women, including transgender women, are excluded from the study because (1) effective HIV preventive interventions for women are likely to differ markedly from those focusing on men (particularly men who have sex with men), both in content and presentation; (2) the individual, socio-cultural and developmental factors associated with HIV risk in MSM are different from those for women; (3) the research questions and issues of relevance for MSM are not relevant or appropriate for women; (4) several effective HIV prevention interventions for women have already been developed, evaluated, and disseminated.

People under age 18 are excluded from the study because (1) effective HIV preventive interventions for teenagers are likely to differ markedly from those focusing on young adults and adults, both in content and presentation; (2) the individual, socio-cultural and developmental factors associated with HIV risk in MSM under 18 are different from those for MSM 18 and up; and (3) the research questions and issues of relevance for MSM aged 18 and up may not be relevant or appropriate for MSM under age 18.

# 15.6 Subject Confidentiality

Our efforts to protect privacy and confidentiality are evident in several areas: study procedures, training, and data management practices.

#### Study procedures

We will collect multiple means of contact with participants at the study visit. For each means of permitted contact, we will leave a generic message about participation in a health research survey at that phone/email/cell phone, etc. Standardized scripts for phone and email contact will

be used (uploaded in the eIRB system for review). Participants are offered the option to receive STI testing results by email or text message; for those who so choose, the results messages will not identify the type of testing, the nature of the study, or the specific test names. Scripts for the return of results by email or text message are included in the "Miscellaneous Documents" section of the eIRB forms.

### **Training**

All study staff will have a 1-hour training on patient privacy and confidentiality. (Section 15.7) Staff will sign a confidentiality agreement (uploaded to eIRB) before having access to any confidential data.

# Data management practices

As described above, personally identifying information will be stored in a separate dataset from case report form data, test results, survey answers, and interview transcripts. Access to the identifying information will be restricted, so that persons who are responsible for scheduling can view contact information and next study visit due date, but no other study data. Similarly, persons who can view study data will only be able to see the study data and the (non-identifying) study ID.

# 15.7 Future Use of Stored Specimens and Other Identifiable Data

No specimens will be stored for future use. Specimens returned for STI testing or TFV-DP testing will be destroyed after laboratory analysis.

Additional data analyses beyond those described in this protocol will be performed. Study staff will continue to only have access to identifiable data only as needed.

#### 15.8 Training

All study staff are required to complete the CITI training course modules on human subjects research, socio-behavioral science, and GCP. Annual refresher training on human subjects is required every 3 years. These requirements are tracked by the Emory IRB, and are verified for all new staff being added to the IRB protocol. Certificates will be retained by the PI and available for review on request by the IRB or NIH staff. Study staff will also receive study-specific training on delivering STI test results, and will have completed CDC's Fundamentals of HIV Prevention Counseling course before providing any test results. All staff sign a confidentiality agreement and receive annual refresher training on protecting human subject's information, PII, and protected health information (PHI).

#### 16 DATA HANDLING AND RECORD KEEPING

#### 16.1 Data Management

Data will be stored in password-protected, encrypted files on Rollins School of Public Health computers and on secure Rollins and SurveyGizmo servers, both HIPAA compliant. SurveyGizmo has a HIPAA Business Associate agreement with Emory University. Databases of participant identifying information (contact information such as names, emails, and phone numbers) will not be linked to databases with participant data. Participant identifying information will only be linked to whether the participant completes study procedures, needs to be re-

contacted, or refuses to participate. The name, e-mail, and phone number of screened men who decline to be scheduled for participation will be removed from the study database after we have asked them questions about why they have a lack of interest in proceeding, unless they request to be contacted for future studies. Access to the identifying information will be on a role-based system: access to identifying information will be restricted to those who need access to perform their work function. Thus, access to identifying information will be restricted to the Project Coordinator, study staff providing counseling/referral services, and 2-3 work study students charged with data entry and scheduling tasks.

# 16.2 Procedures for Prevention and Addressing Breaches of Confidentiality

The main approach to preventing breaches of confidentiality is to maintain identifying participant information in a single location at each site and to use a non-personally identifying study ID to store all other study data.

The study will use a HIPAA-compliant web-based platform entitled Study Management and Retention Toolkit (SMART), which is a SaaS (Software as a Service) based mobile application aiding studies with various aspects of participant recruitment, study implementation, and retention. The application has the ability to securely manage participant information across multiple studies and customers simultaneously, stratifying participant information by study and site. SMART includes an admin web portal and a participant facing mobile app (optional), which allows for secure messaging, study calendar management, self-scheduling by participants, secure photo uploads, and longitudinal tracking of participants from screening to study completion. The ability to designate specific roles to all SMART users allows for greater control around permissions and accessibility to participant information. Users can even be limited to a reporting only role, which allows for study oversight through real time aggregate reporting, but no access to PHI. SMART is a licensed service of the Center for AIDS Research (CFAR) at Emory University, Prevention Science Core. Utilization of the mobile app is optional and the admin web portal will fully function without it.

The following information outlines the security of the three SMART components: (1) the admin web portal, (2) the participant app, and (3) a web service that acts as a liaison between the mobile app and the study database.

Admin Web Portal. The admin web portal is a web-based application developed using Microsoft .NET technologies. It uses SQL server as backend database. The application requires two servers to host: (1) Web server [Windows server with IIS] and (2) SQL server [Standard or Enterprise version]. Both these servers are to be placed behind a firewall. Web server will have a public IP to access the server using VPN. SSL certificate is to be installed on the web server. The admin website will be rendered over SSL (https). The application uses form authentication (no integrated authentication such as AD). All passwords are stored encrypted within the database. System will also be using database level encryption, which will prevent any copying of information from one database to another. Web application also uses an automatic logout feature after a certain period of inactivity. By default, the inactivity duration is set to three minutes.

Study staff can only first gain access to the admin web portal if granted by a study or site administrator. Their assigned user role will determine their permissions to perform different actions and even view PHI. Email notifications are sent from the system (without the need to login) when: (1) a staff member requests to reset their password, (2) role assignments to a study are made, (3) an event/visit staff are scheduled to work is nearing, (4) a new task is

assigned to a staff member, or (5) they are designated as a staff member to receive alerts of positive test results. All participant communications are performed using secure messaging through the message center (inbox) implementation within the mobile app. If the mobile app is not utilized by a study, communications are sent as standard email or text messages to participants.

Mobile App. The mobile app, developed natively for iOS and Android platforms and available for free in the App Store and Google Play Store, is an optional feature the study can utilize for selfscheduling, communication, photo uploads, and updating contact information. The study will indicate during the initial setup within the admin web portal whether the participant mobile app is utilized or not. If the app is utilized, participants will receive download instructions after their information is entered into the admin web portal. Only participants listed in an active study who validate their email or phone number against the contact information listed in the admin web portal will be able to proceed into the app. For validation, the app uses both traditional form authentication as well as social login (Facebook and Google). The social login feature will only work if the email associated with either social account matches the contact information within the admin web portal. The app does not request anything other than basic information from these authentication services. Participants cannot "remember" their password on the mobile device for automatic logins to ensure privacy. All participant data and activity status is maintained within a secure and encrypted SQL Server database. To create the connection between the admin web portal and the mobile app, each participant is assigned a unique ID within the application, which is associated with their login credentials. When a participant has been successfully authenticated through the mobile app, the admin web portal will send their specific information to their phone through the established secure session (web APIs using SSL). The app will not store the information presented locally on the phone. Local data storage is used only for storing some minimal non-PHI information, such as app settings. The mobile app implements an automatic logout when there is inactivity for more than three minutes. If a participant should need to re-download the app on a new device, login and password authentication will be required again.

The mobile app has push notifications that are primarily used for reminders and notifications of new messages. Push notifications displayed on the participant's phone will be generic in nature and not contain any PHI. Reminders and notifications within the mobile app inbox will also be generic in nature, with any message containing sensitive information requiring a pin, established during registration as a secondary authentication, to open within the mobile app. Firebase cloud messaging service is used as a communication channel for these notifications. No PHI is passed through Firebase. Push notifications are customizable in the study setup, and samples of system notifications include: "You have a new message in your inbox," "You have an upcoming event for March 7, 2018," and "You have a pending task."

Web Service. A web service will also be hosted on the web server. This service is used by the mobile application to retrieve and store data. The service will utilize secure socket layer (SSL) for communication.

The HealthMindr app itself also has protections for breach of confidentiality. The app requires re-authentication through a user-selected password or proxy (e.g., fingerprint authentication) if the app has been navigated away from, or if more than 5 minutes pass without interaction. This is similar to security functions that are in place for other apps with sensitive information (such as banking or apps allowing access to medical records).

To minimize risks to confidentiality, we will provide study data with all appropriate physical and operational security protections. Paper-based data will be stored in a locked cabinet in a locked office, and all data files will have encryption and strong password protection. Access to data will be on a role-based standard; only those study staff, such as principal and co-investigators, data managers, data analysts, study staff (public health program associates and assistant or associate directors of research), and graduate research assistants, who require access to identifying data to complete their study-related roles will be allowed access. Any photographs (i.e., PrEP prescriptions or bottle labels) will be sent to study staff securely through the app. SurveyGizmo, the electronic platform for self-interview, has a HIPAA business partner agreement with Emory. All study staff will complete CITI course modules on human subjects research ethics, socio-behavioral research, and good clinical practice (GCP), will be trained in security and confidentiality procedures, and will sign a confidentiality agreement before receiving access to any participant data. Any breaches in confidentiality will immediately be reported to the PI and to the IRB. Based on the PI and IRB's recommendation, staff may be retrained or receive disciplinary action.

Study staff will follow procedures to minimize indirect disclosure that a participant is participating in an HIV-related research study, or a study that enrolls MSM. For each mode of contact information, including email, telephone, text, and voicemail, we will ask specifically whether anyone else potentially has access to that mode of communication, and if it is acceptable to leave a non-specific message about participation in a health study. No study-related messages to the participant will ever mention HIV prevention or the nature of the research study. Additionally, all scripts for email, text message, and telephone contact with participants will be reviewed and approved by the Emory IRB before being used for contact with participants.

### 16.3 Data Capture Methods

Data collected through the mobile app: Participants will use a mobile phone app to get information about HIV prevention and referrals to local services. As participants use the app, data about which features they used are entered directly by the participant in the process of interacting with the study app or control app.

Data collected through the online survey interface: Participants will also take surveys through an online survey portal. Data are collected directly on the private server as participants respond to questions. Data will be identified in the system through a Study ID. Surveys are conducted using a secure (https://) webpage, which means that data entered by participants are encrypted before they are sent through the internet, and are decrypted once received by the survey hosting site. The link between the participant and the participant contact information is held by Emory University research staff.

Data collected through mail in-specimens: Participants who request STI testing will mail in urine, rectal swab, throat swab, and blood specimens for testing. All mailed-in specimens will be labelled with a unique ID number, which will be the same for all tubes in one specimen collection kit, i.e. the box ID. Participants will be asked to register this box ID using a unique URL linked to their study ID. This will allow linkage of specimen test results back to the correct participant.

Electronic CRFs through DFexplore will be used for any data collection unable to be completed through the surveys and HealthMindr database, such as study withdrawal or adverse events. Data entry will be conducted by IRB-approved staff. Forms are double checked, and

electronically verified for possible discrepancies. Any possible discrepancies are resolved by rereview by a third, more senior data manager.

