#### 4 STUDY DESIGN

We will conduct a randomized controlled trial (RCT) with two arms. Participants in the intervention arm will receive access to the HealthMindr app with basic prevention services (HIV test planning and test locators; risk assessment; HIV treatment locators; and condom, HIV test kit, and at-home STI specimen collection kit distribution) plus monthly PrEP eligibility assessments, PrEP provider locator, enhanced information about PrEP, and referrals to local PrEP navigators. The app also provides links to health insurance exchanges, where men can seek health insurance (all cities) or payment assistance programs. The control arm will be standard of care (receive baseline survey, followed by referral to existing online PrEP and HIV prevention information; with a mobile-phone administered attention control survey about diet and exercise (and PrEP initiation) of the same length as the monthly PrEP assessment given to the intervention arm, to maintain the same monthly frequency of contact with control participants. Control arm participants will not have access to the active app.

Study participants are followed for 12 months with outcome measurements occurring in both arms at 3-month intervals and monthly brief surveys to assess PrEP uptake and reassess PrEP eligibility (intervention arm) or assess diet and exercise (control arm). Surveys will be distributed to all participants through the mobile app at baseline and quarterly. Participants will specify their preference for communication media in the baseline survey. Quarterly surveys will last approximately 30 minutes; to limit survey duration, some non-labile survey elements will not be assessed at each time point. Quarterly surveys are identical for men in both arms, except the final survey includes questions on acceptability only for men who used the app. Surveys are smartphone-optimized so that they may be completed on participants' phones. The survey

measures represent a comprehensive set of previously validated measures that will characterize the population, allow for assessment of adequacy of randomization, document important outcomes, and allow for exploration of possible moderating factors. A summary of measures is included in Figure 2.

Figure 2. Measures to be assessed in participant surveys.

Outcomes	Community & Network Characteristics
PrEP Awareness/Use/Efficacy	Health Care Environment
Participant has heard of PrEP	Payer source: insurance coverage, out-of-pocket

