Every three months, participants will be asked to complete a follow-up survey similar to the initial baseline survey. The follow-up survey will include questions on demographic characteristics, HIV and STI testing history and status, and condom use, PrEP use and adherence, knowledge, perceptions, beliefs, intents, communication with sex partners, substance use, mobile phone and data usage, access to internet and information, as well as psychosocial cofactors. If the participant has any questions regarding study activities, they will be connected with study staff. Study staff will handle any research related questions or issues with the participant.

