#### 9 ASSESSMENT OF SAFETY

# 9.1 Specification of Safety Parameters

All adverse events reported will be assessed by the PI for the study site in which the participant was enrolled for the severity, expectedness and relatedness, using the criteria listed below.

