#### 9.1.1 Adverse Events

- 1. Participant report of loss of confidentiality through the app or its functions
- 2. Participant report of loss of confidentiality through delivery of prevention supplies or commodities
- 3. Participant report of access by others to protected health information through the app or study procedures.
- 4. Participant report of disclosure of status as a research participant due to study-related reminders (from app, phone calls, emails, or text messages).
- 5. Participant report of discomfort or injury due to use of provided specimen collection materials (e.g., finger stick for syphilis testing, self-administered rectal swab or pharyngeal swab).
- 6. Disclosure of personal information about health, sexuality or sexual practices that results in physical violence or threat of violence.
- 7. Disclosure of personal information about health, sexuality or sexual practices that results in adverse effects on employment

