#### 9.1.2 Serious Adverse Events

- 1. Suicidal behavior or intention, including but not limited to following learning the results of study-provided tests (e.g., HIV tests, STI tests)
- 2. Any event that results in death, is life-threatening, results in persistent or significant disability/incapacity, or requires hospitalization or prolongation of existing hospitalization

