### Management and storage:

Data within the study app: Data are stored in a secure, HIPAA compliant server in the cloud. Access to app data are password protected, and access is role-based. Access to participant data will be limited to study staff approved by IRB in each site, comprising principal and coinvestigators, data managers, data analysts, study staff, and graduate research assistants. Software developers will have access to administrative aspects of the management portal, but will not routinely have access to links to Study IDs or personally identifying information (PII). In the case of a "need to know" for study related purposes (for example, duplicate or corrupted files, need to examine specific records to troubleshoot app or data functions) temporary access can be granted to developers, whose access will be limited to the specific records required to resolve the problem. Any developer who needs such access will be required to complete CITI training, complete a PRISM data confidentiality form, and be added to the IRB protocol. Access to participant-identifying information will be removed after the specific problem is resolved.

Security protections of identifying information: Identifying information will be held in a secure study database at each study site. Identifying data will be stored in the System for Management and Reporting of Trials (SMART), an IT solution provided by the Emory University CFAR and hosted on a secure cloud-based server at each of the three participating institutions. Access is role-based, and is protected through institutional firewalls and password procedures at Emory University, George Washington University, and the University of Mississippi Medical Center, respectively.

Data collection through Case Report Forms:

Collection: Data will be entered in DFexplore on electronic CRFs for enrollment, randomization, study stop, and reportable events. The records will be stored by Study ID and not include participant names.

Management and storage: Data will be stored in a cloud-based LINUX Microsoft Azure server managed by DF/net, the company of that manages DFexplore. The data will then be downloaded onto secure Emory servers. Emory has BAA with DF/net and data will only be accessible to persons who have been provided with login and passwords.

Data collection through online surveys:

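### The plan describes no scheduled question about study-caused harm, so adverse-event counts will be incomplete to an unknown degree

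*Combined protocol and SAP*

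**What the plan says.** Section 16.3 routes to DFexplore forms, completed by study staff, "any data collection unable to be completed through the surveys and HealthMindr database, such as study withdrawal or adverse events". Section 16.4 lists what those forms cover: "Data will be entered in DFexplore on electronic CRFs for enrollment, randomization, study stop, and reportable events". No form for a scheduled safety enquiry is among them.

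Section 9.1 begins from events already known: "All adverse events reported will be assessed by the PI for the study site". Section 11 has the principal investigator review whatever adverse event reports arrive. The first item of section 9.1.1 is "Participant report of loss of confidentiality through the app or its functions", and items 2 to 5 are likewise framed as participant reports. Items 6 and 7 (disclosure leading to violence or to harm at work) are not worded that way. Among the serious events, section 9.1.2 lists "Suicidal behavior or intention, including but not limited to following learning the results of study-provided tests".

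On the surveys, section 6.1.1 states: "The follow-up survey will include questions on demographic characteristics, HIV and STI testing history and status, and condom use, PrEP use and adherence", and continues through knowledge, beliefs, substance use, phone use and psychosocial factors. Section 4 adds: "Quarterly surveys are identical for men in both arms, except the final survey includes questions on acceptability", and those extra questions go only to app users. Section 7.3 gives the monthly content as a PrEP assessment (app arm) or a diet and exercise survey (control arm), plus PrEP initiation and adherence questions.

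**The concern.** The harms the protocol chose to list are mostly private: being outed by a parcel or a reminder, someone else reading health information, violence, trouble at work, injury from a swab or finger stick. In most cases only the participant can know of them. Consent is online, surveys run through the app, specimens travel by mail and interviews are online, so no clinic visit supplies a routine occasion to ask. If the surveys do not ask either, capture rests largely on a man deciding to contact staff.

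Oversight depends on those same reports. Section 10 plans no DSMB and leaves monitoring to the principal investigator and the IRB. The 24-hour clock for serious events in section 9.2.1 starts when the event reaches the investigator. Section 12 plans no adverse-event analysis, so nothing later in the plan would show how much was missed. At stake is the reading of the safety data; the primary PrEP-uptake comparison is unaffected.

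**Working it through.** **Step 1. Is there any scheduled enquiry about study-caused harm?** These are the routes by which an event could reach staff without a man volunteering it:

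- *Quarterly surveys* (section 4 with Figure 2; section 6.1.1). The nearest items are enacted stigma and discrimination, the CES-D depression scale and recent incarceration. They are listed as participant or social characteristics. None is tied to the study, and no link from them to an adverse-event form is stated.
- *Monthly surveys* (section 7.3). No harm item is described.
- *Withdrawal* (sections 5.4 and 7.4). Reasons are asked, but only of men who say they want to leave.
- *Retention contacts and searches* (section 5.2.2). Staff contact men who miss surveys. Jail and death-registry searches apply to men lost to contact. No harm question is described.
- *Positive STI result calls* (section 8.2). Offered testing is in the intervention arm; no adverse-event enquiry is described.
- *Breaches of confidentiality* (section 16.2). These go to the principal investigator and IRB once known to staff.
- *In-depth interviews* (section 7.6). At most 30 + 20 = 50 men, or 50/680 = 7.4%, plus any who seroconvert. They ask for good and bad features of the app, not about the section 9.1.1 events.

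So other routes exist, but each is narrow and none asks all participants about the seven listed events.

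**Step 2. What would a low count mean?** The documents give no expected event rate, capture rate or safety precision target, so there is no figure of the plan's own to reproduce. The calculation below is illustrative.

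Inputs: 680 men (section 4.1), randomized 2:1 (section 5.3.1), so 680 × 2/3 ≈ 453 in the app arm. Let *r* be the true risk and *s* the share of events that reach staff. The value of *s* is an assumption, shown at 100%, 50%, 25% and 10%.

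The observed count carries information only on the product *r × s*. With zero reports in *n* men, the one-sided 95% upper bound solves (1 − r·s)^n = 0.05, so

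r = [1 − 0.05^(1/n)] / s.

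For n = 453, 1 − 0.05^(1/453) = 0.0066. For n = 680 (both arms), 1 − 0.05^(1/680) = 0.0044.

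| Assumed capture *s* | Bound, 453 app-arm men | Bound, all 680 men |
|---|---|---|
| 100% | 0.66% | 0.44% |
| 50% | 1.3% | 0.88% |
| 25% | 2.6% | 1.8% |
| 10% | 6.6% | 4.4% |

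Conversely, suppose the true risk is 2% in the app arm, which is 453 × 0.02 ≈ 9 affected men. The chance that staff hear of none is (1 − 0.02·s)^453:

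- s = 100%: 0.98^453 = 0.01%
- s = 50%: 0.99^453 = 1.1%
- s = 25%: 0.995^453 = 10%
- s = 10%: 0.998^453 = 40%

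These figures treat all 453 men as followed throughout. If only 80% were (section 12.2 assumes 20% attrition), n ≈ 0.8 × 453 = 362 and the full-capture bound becomes 1 − 0.05^(1/362) = 0.82%.

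**The case against.** The strongest reply is that the absence is inferred. The survey instruments are not in the documents, Figure 2 is presented as a summary, and the survey list in section 6.1.1 ends in an open category. Section 16.3 says where adverse events are recorded, which is not the same as how they are elicited. Its own sentence also names study withdrawal, yet section 7.4 does use a short survey for withdrawal reasons. This stands as a limit on certainty. It does not remove the point: section 16.3 treats adverse events as something the surveys cannot complete, and no section describes a prompt.

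Three stronger readings are tempting, and the documents do not support them.

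- *That the protocol rests minimal risk on a low event count.* Section 15.1.1 calls the risks minimal as a prior ethics judgement. No section ties that judgement to observed events, and no safety objective or analysis is planned. The concern is only how a future low count might be read.
- *That events are seen only if volunteered, and the surveys ask about everything but harm.* The other routes and the stigma, depression and incarceration items in the working show both statements are too absolute.
- *That unequal staff contact biases the comparison between arms.* This is possible but not shown. Parcels and kits are mainly exposure to items 2 and 5 of section 9.1.1, so more such reports in the app arm could be real harm. Control men have the same monthly frequency of contact, the same quarterly surveys and the same retention procedures.

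It is also fair to say that the trial supplies no medication, that section 10 gives a reason for light monitoring, and that nothing here contradicts another statement in the plan.

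**Conclusion.** The point holds in this form: the plan as written specifies no solicited collection of study-caused harm, so adverse-event counts will be incomplete to an unknown degree and a low count would be weak evidence of low risk. It rests on the described survey content being complete in this respect, which sections 16.3, 9.1 and 11 support but which the instruments themselves would have to confirm.

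Only the full-capture bound (0.66% for zero events in about 453 app-arm men) is free of an assumed capture share. The rise to 1.3%, 2.6% or 6.6% shows how strongly the reading depends on that share; it does not estimate the share in this trial. This is a cheap improvement to safety ascertainment and does not threaten the trial's main result.

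**What to change.** First check the quarterly survey instruments for an existing harm question. If there is none, then for the month 3, 6, 9 and 12 surveys still to be sent:

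1. Add a short block mirroring the seven items of section 9.1.1, worded identically in both arms. It could ask whether, since the last survey, taking part in the study has led to any of the listed events.
2. Have any positive answer alert staff automatically, so that the existing event form and the severity and relatedness steps of sections 9.1.3 and 9.1.4 begin.
3. Add to section 12 a tabulation of adverse events by arm, with prompted and spontaneous reports shown separately and the number of men who answered the block as the denominator for prompted events.

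If all surveys have already been sent, as the recontact procedure in section 14.1 suggests may be true for some men, only the separate labelling remains: describe the counts as spontaneous reports and do not offer a low count as evidence of safety.

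The cost is about 1 minute on a survey of roughly 30 minutes that every participant already receives, more event forms for existing staff, and probably a higher adverse-event count, which should be explained as better ascertainment. Men who skip surveys will still be missed, so capture will improve but not become complete.
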